6.2 PRIMARY EFFICACY VARIABLE

Data will be analyzed according to clinical status at day 28. Outcome will be the proportion of patients who are alive and free of respiratory failure (no use of HFNC, NIPPV, Intubation). All other patients, those on HFNC, NIPPV, or mechanical ventilation, or dead, will be assessed as

Tenecteplase-Icahn School of Medicine at Mount Sinai
Protocol ML42492

37

failures for the purposes of the primary analysis. In the case of missing data, a last carry forward methodology will be used.

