2.2 PRIMARY EFFICACY OUTCOME

The primary efficacy outcome will be the proportion of patients alive and free of respiratory failure (defined as not requiring non-rebreather, high-flow nasal cannula, non-invasive positive pressure ventilation, or mechanical ventilation) at 28 days.

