2.3 STUDY OUTCOMES

The following outcomes will be tracked for the trial:

Primary outcome is: the proportion of patients alive and free of respiratory failure (not requiring non-rebreather, high-flow nasal cannula, non-invasive positive pressure ventilation, or mechanical ventilation) at 28 days

- A. Primary safety outcome: Occurrence of intracranial bleeding or major bleeding (Definition: A bleeding episode leading to hemodynamic compromise requiring emergency intervention (such as replacement of fluid and/or blood products, inotropic support, or surgical treatment), or life-threatening or fatal bleeding) within 72 hours of randomization. All outcomes will be assessed in a blinded fashion by the DSMC/CEC.
- B. Secondary outcomes include: 14-day in-hospital mortality, 28-day mortality, ventilator-free days, respiratory failure-free days (not requiring NRB, HFNC, NIPPV, or mechanical ventilation), vasopressor-free days, vasopressor requirements at 24 and 72 hours, P/F ratio at 24 hours and 72 hours, ICU-free days, hospital length of stay, new renal failure, need for renal replacement therapy
- C. Mortality: given a high mortality rate amongst this patient population, patients who die will be included in statistical analysis. Variables of interest will be calculated until the point these patients expire.

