3.3 RATIONALE FOR STUDY DESIGN

This is a phase II dose escalation study intended to evaluate the potential safety and efficacy of tenecteplase for the treatment of COVID-19 associated respiratory failure. This study is not powered for significance, but is instead designed to provide an estimate of the potential benefit-signal and better inform a subsequent phase III RCT.

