3.3.2 Rationale for Patient Population

This patient population has been chosen because they have objective indications of respiratory failure (intubation, NRB, HFNC, or NIPPV) but that failure is recent in onset. There has been increasing literature demonstrating the progressive thrombosis that occurs in multiple organ systems during COVID-19, including the lungs. By administering tenecteplase to this early stage respiratory failure population, who also have demonstrable thrombosis occurring (as indicated by their D-dimer) we hope to reverse the progressive pulmonary thrombosis that is occurring and thereby improve their outcome.

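### Section 6.2 leaves the non-rebreather mask out of the primary endpoint's scoring rule, contradicting Sections 2.2 and 2.3

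*Combined protocol and SAP*

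**What the plan says.** Section 2.2 defines freedom from respiratory failure, the core of the primary efficacy outcome, with four supports named: "defined as not requiring non-rebreather, high-flow nasal cannula, non-invasive positive pressure ventilation, or mechanical ventilation) at 28 days". Section 2.3 repeats the same four for the primary outcome. It uses them again for a secondary outcome, "respiratory failure-free days (not requiring NRB, HFNC, NIPPV, or mechanical ventilation").

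Section 6.2 sets the scoring for the primary analysis. Success is "Outcome will be the proportion of patients who are alive and free of respiratory failure (no use of HFNC, NIPPV, Intubation"). The failure rule is "All other patients, those on HFNC, NIPPV, or mechanical ventilation, or dead, will be assessed as" failures. NRB appears in neither list. Section 6.2 then adds: "In the case of missing data, a last carry forward methodology will be used".

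Elsewhere NRB is treated as respiratory failure. Section 4.1.1 admits patients on NRB, and Section 3.3.2 counts it among the "objective indications of respiratory failure (intubation, NRB, HFNC, or NIPPV"). Section 6.1 defines the good outcome with the same general phrase but lists no devices.

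**The concern.** The primary endpoint has two scoring rules that disagree about one group: patients alive at day 28 whose highest support is NRB. An analyst working from the lists in 6.2 scores them as successes; one working from 2.2 scores them as failures. Because NRB qualifies a patient for entry, someone enrolled on NRB and unchanged at day 28 would be a treatment success under the literal 6.2 rule. The carry-forward rule extends this to any patient with a missing outcome whose last recorded status is NRB.

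Section 3.3 says: "This study is not powered for significance, but is instead designed to provide an estimate of the potential benefit-signal". What is at stake is therefore mainly the success rates and their difference, which are what this trial is meant to hand to phase III. If the conflict is settled only after the data are in, the scoring rule could be chosen with the results known.

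**Working it through.** **1. The definitions side by side**

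| Place | NRB | HFNC | NIPPV | Mechanical ventilation / intubation |
|---|---|---|---|---|
| 2.2 primary outcome | named | named | named | named |
| 2.3 primary outcome | named | named | named | named |
| 2.3 respiratory failure-free days | named | named | named | named |
| 4.1.1 entry criterion | named | named | named | named |
| 3.3.2 population rationale | named | named | named | named |
| 6.2 success definition | **absent** | named | named | named |
| 6.2 failure list | **absent** | named | named | named |

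Take a patient alive on NRB at day 28. Under 6.2 the patient is alive and uses no HFNC, NIPPV or intubation, so the success wording is met and the failure list does not apply. Under 2.2 the patient requires NRB and fails.

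**2. The plan's own power figure**

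Inputs from 6.1: 40 v 20 patients, 15% control rate, 35-point difference (so 50%), two-sided 0.05, Fisher's exact test. Summing binomial probabilities over all outcomes with either Fisher tail at or below 0.025 gives 71.4% (stated: about 70%). The minimum-likelihood two-sided p-value gives 74.5%. For 20 v 20 both variants give 57.3% (stated: about 55%). The planning figures are sound and the omission does not affect them, provided the 15% and 50% were set under the 2.2 definition, which 6.1 does not say.

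**3. Shift per reclassified patient**

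- One arm of 20: 1/20 = 5.0 percentage points.
- Pooled tenecteplase group of 40: 1/40 = 2.5 percentage points.

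**4. What this can do to a test result (illustration only)**

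Two-sided Fisher p-values, first under 2.2 and then with NRB patients moved to success:

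| Comparison | Under 2.2 | Patients moved | Under literal 6.2 |
|---|---|---|---|
| Single dose | 10/20 v 3/20, p = 0.041 | 1 control | 10/20 v 4/20, p = 0.096 |
| Single dose | 9/20 v 3/20, p = 0.082 | 1 treated | 10/20 v 3/20, p = 0.041 |
| Single dose | 10/20 v 3/20, p = 0.041 | 1 per 20, both arms | 11/20 v 4/20, p = 0.048 |
| Single dose | 10/20 v 3/20, p = 0.041 | 2 per 20, both arms | 12/20 v 5/20, p = 0.054 |
| Pooled | 17/40 v 3/20, p = 0.044 | 1 per 20, both arms | 19/40 v 4/20, p = 0.051 |
| Pooled | 20/40 v 4/20, p = 0.029 | 1 per 20, both arms | 22/40 v 5/20, p = 0.032 |
| Pooled | 20/40 v 4/20, p = 0.029 | 2 per 20, both arms | 24/40 v 6/20, p = 0.054 |
| Pooled | 20/40 v 3/20, p = 0.011 | 1 per 20, both arms | 22/40 v 4/20, p = 0.013 |

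A borderline result can cross 0.05 in either direction; a clear one does not.

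**5. Effect on the planned difference (assumed range)**

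Let a fraction *q* of those failing under 2.2 in each arm be alive on NRB. The rates become 0.15 + 0.85*q* and 0.50 + 0.50*q*, so the difference is 0.35 − 0.35*q*.

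| *q* | Control | Tenecteplase | Difference | Pooled power (each tail ≤ 0.025) |
|---|---|---|---|---|
| 0 | 15.0% | 50.0% | 35.0 points | 71% |
| 5% | 19.3% | 52.5% | 33.3 points | 63% |
| 10% | 23.5% | 55.0% | 31.5 points | 55% |
| 20% | 32.0% | 60.0% | 28.0 points | 42% |

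The documents give no value of *q* and do not say it would be equal between arms. This is a range, not a forecast.

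**The case against.** The documents point to one intended definition. Section 2.2 is headed as the primary efficacy outcome, says what respiratory failure is defined as, and names NRB; 2.3 agrees. Section 6.2 keeps the phrase about being free of respiratory failure, so its parenthesis could be incomplete shorthand, with its failure rule for all other patients sweeping in the rest. On that reading a careful analyst would apply 2.2, and this is only a wording correction.

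Much of this stands: the omission does look like a slip. But 6.2 does not leave the phrase open. It restates the meaning without NRB and then lists the failures, again without NRB. The reference to all other patients does not help, because it covers only those outside a success definition that the NRB patient literally meets.

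It is also fair to say that the p-values are a side issue. Fisher's test is named only in the power statement in 6.1, not in 6.5; the trial is not powered for significance; and several nearby cases do not cross 0.05. The firm quantity is the per-patient shift.

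**Conclusion.** The concern holds, and the text must be corrected. Section 6.2 as written gives a primary-endpoint rule that contradicts 2.2 and 2.3, and nothing says which prevails. The contradiction is textual and rests on no calculation. The firm size is 5 percentage points per affected patient in a 20-patient arm and 2.5 in the pooled 40. The total effect on the estimated difference, and its direction, are unknown because no day-28 NRB rate is given. The shrinkage and power figures above depend on assumed rates, and the p-values also assume that Fisher's test is used for the comparison.

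**What to change.** In 6.2, change the success parenthesis to *no use of NRB, HFNC, NIPPV or mechanical ventilation*, and the failure list to *those on NRB, HFNC, NIPPV or mechanical ventilation, or dead*. This also replaces the word intubation with the term used in 2.2. A sentence stating that the definition is that of 2.2 would settle any remaining difference between using a support and requiring it. A carried-forward NRB status is then a failure too.

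Also check that the day-28 ordinal form can identify NRB use. Under 4.5.6 the ordinal scale is the only day-28 item required for discharged patients. Footnote ** of the Appendix 1 flowchart lets daily respiratory-status recording stop after a 2-point ordinal improvement, although 4.5.5 asks for it daily. The scale's categories are not given, so this is a check and not a stated defect.

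The cost is two short edits in 6.2 and possibly one added form field. Sample size and alpha do not change. The stated power stands if the 15% and 50% planning rates were set under the 2.2 definition, which 6.1 should confirm.

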6. STATISTICAL CONSIDERATIONS

6.1 DETERMINATION OF SAMPLE SIZE

Assuming a total of 60 subjects enrolled with a 2:1 ratio in the tenecteplase:control arms and a good outcome rate of 15% in the control arm, this study has approximately 70% power to detect an absolute difference of 35% in the good outcome rate between the combined tenecteplase arms (40 patients) and the control arm (20 patients) and approximately 55% power to detect an absolute difference of 35% between each of the tenecteplase arms (20 patients) and the control arm (20 patients), at the 2-sided 0.05 significance level based on the Fisher's exact test. Good outcome rate is defined as the proportion of patients who are alive and free of respiratory failure at 28 days. If the true rate of symptomatic ICH or major bleeding requiring transfusion is 3%, the chance of observing at least one of these events in 20 patients is at least 45%. The chance of observing at least one event in 20 patients increases to at least 70% if the true event rate is 6%.

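### Section 6.2 scores the primary endpoint by device use where 2.2 and 2.3 define it by need, so read literally it counts as a success a patient alive at Day 28 whose support was withdrawn or withheld as a limit of care

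*Combined protocol and SAP*

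**What the plan says.** Section 2.2 gives the endpoint as the proportion alive and free of respiratory failure at 28 days, the latter "defined as not requiring non-rebreather, high-flow nasal cannula, non-invasive positive pressure ventilation, or mechanical ventilation". Section 2.3 repeats it: "the proportion of patients alive and free of respiratory failure (not requiring non-rebreather, high-flow nasal cannula", followed by the same remaining supports.

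Section 6.2 is where patients are actually scored. It sets the time point ("Data will be analyzed according to clinical status at day 28") and then gives two lists. Success is "alive and free of respiratory failure (no use of HFNC, NIPPV, Intubation". The next sentence gives the failures: "All other patients, those on HFNC, NIPPV, or mechanical ventilation, or dead, will be assessed as" failures in the primary analysis.

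Section 6.2 therefore differs from 2.2 in three ways:

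- *Use of* and *on* replace *requiring*, in both sentences.
- *Intubation* replaces *mechanical ventilation*, in the success sentence only.
- The non-rebreather mask is missing from both sentences. That is a separate and plainer conflict, mentioned here because one edit should repair both.

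**The concern.** Need and use part company when a patient needs support but does not receive it. The obvious case is a limit of care: ventilation or high-flow oxygen is stopped or declined, and the patient is alive on Day 28 with no device in place. On the natural reading of 2.2 this patient still requires support and has not succeeded. Under both sentences of 6.2 no device is in use, so the patient is a success.

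A patient with one of the worst living outcomes would then count the same as one who has recovered. The primary endpoint is a single binary status in 40 versus 20 patients, so individual classifications are visible in the result. If survival or the use of care limits differs between arms, the error would not be balanced. The trial exists to estimate a benefit signal for a phase III study (3.3), so the estimated rate matters even without a formal claim of significance.

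The Day-28 schedule does not clearly protect against this. Section 4.5.6 collects respiratory status at Day 28 only if the patient is still admitted. A patient who has left hospital, for instance to hospice, has the ordinal scale, and the available text does not give its categories.

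**Working it through.** **Passages side by side.** All patients below are alive at Day 28 unless stated.

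| Status at Day 28 | 2.2 and 2.3 (need) | 6.2 (use) |
|---|---|---|
| Dead | failure | failure |
| On HFNC, NIPPV or a ventilator | failure | failure |
| No support, none needed | success | success |
| No support because it was withdrawn or withheld, still in respiratory failure | failure on the natural reading; *requiring* is not defined | success, read literally |

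Only the last row separates the two rules on this point.

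**Inputs** (6.1). "Assuming a total of 60 subjects enrolled with a 2:1 ratio in the tenecteplase:control arms", so 40 v 20; control rate 15%; absolute difference 35 points, so 50% on tenecteplase; two-sided 0.05; Fisher's exact test. The planned result is 0.50 × 40 = 20 successes v 0.15 × 20 = 3.

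**The plan's own figures.** The plan states power of about 70% (40 v 20) and about 55% (20 v 20). The arcsine approximation with continuity correction gives 70.3% and 54.8%, so both are reproduced. Exact enumeration, which sums the binomial probability of every pair of counts with Fisher p ≤ 0.05, gives 74.5% and 57.3%. This point disputes neither figure. Exact values are used below.

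**Weight of one patient.** 1/20 = 5 points in control; 1/40 = 2.5 points in the combined tenecteplase arms.

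**Effect on the test at the planned result** (two-sided Fisher). The counts of misclassified patients are assumptions.

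| Wrongly passed | Tenecteplase v control | p |
|---|---|---|
| none | 20/40 v 3/20 | 0.011 |
| 1 control | 20/40 v 4/20 | 0.029 |
| 2 control | 20/40 v 5/20 | 0.096 |
| 1 tenecteplase | 21/40 v 3/20 | 0.006 |
| 2 tenecteplase and 1 control (5 points in each) | 22/40 v 4/20 | 0.013 |
| 4 tenecteplase and 2 control (10 points in each) | 24/40 v 5/20 | 0.014 |

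**Effect on exact power, 40 v 20.**

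- No error (50% v 15%): 74.5%.
- 5 points added in control only (50% v 20%): 56.6%.
- 5 points added in both arms (55% v 20%): 70.1%.
- A share m of true failures wrongly passed in each arm: control becomes 0.15 + 0.85m and tenecteplase 0.50 + 0.50m. At m = 2% the rates are 51.0% v 16.7%, difference 34.3 points, power 71.1%. At m = 5% they are 52.5% v 19.25%, difference 33.25 points, power 66.2%.

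**The case against.** The best defence is that the governing phrase in 6.2 is alive and free of respiratory failure, which 2.2 has already defined, and that the brackets are shorthand. On that view a scorer would go back to 2.2. Section 2.2 also never defines *requiring*, so a patient who has declined intubation is not settled there either. The case is narrow as well: the patient must be alive, off support and still in respiratory failure on one particular day. The cited mortality of up to 88% in intubated patients, set beside an assumed 15% success rate, leaves few living failures to misclassify among such patients.

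Much of this stands. The group is small and its size is unknown, and copying 2.2 alone would not fully settle the case. But 6.2 is the scoring rule, both of its sentences are worded by use, and nothing in it sends the scorer back to 2.2. A lack of definition in 2.2 is a reason to add a sentence, not a reason to leave 6.2 as it is.

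A reader might infer more than the documents support:

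- **Tracheostomy.** *Intubation* might seem to misclassify these patients. A patient ventilated through a tracheostomy fails under the second sentence of 6.2, which names mechanical ventilation. A patient weaned from the ventilator is in no failure list, and fails only if the tube itself counts as intubation. The two supposed errors need opposite meanings of the word. Section 3.3.2 uses intubation for what the entry criteria in 4.1.1 call mechanical ventilation, so the shorthand reading is the likely one.
- **ECMO.** Neither 2.2 nor 6.2 mentions it, so there is no conflict between them to report.
- **A lost result.** Two wrongly passed controls take p to 0.096, but only if every error falls in control. The documents give no mechanism for that, and 3.3 says the study is not powered for significance.

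**Conclusion.** The point holds in a limited form. Sections 2.2 and 2.3 define the primary endpoint by need, and 6.2 scores it by use. Read literally, 6.2 passes a patient alive at Day 28 whose support was withdrawn or withheld while still needed.

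The likely effect is small. Each such patient is worth 5 points in control or 2.5 points in the combined tenecteplase arms. One in control moves p from 0.011 to 0.029; equal 5-point errors in both arms leave p at 0.013 and exact power at 70.1%. Larger effects need the errors to fall in one arm.

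This rests on two assumptions. One is the natural reading of *requiring* as covering support that is needed but not given. The other is the number of such patients, for which the documents give no figure.

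The mismatch between *Intubation* and *mechanical ventilation* is a wording alignment. It does not show that tracheostomy patients are misclassified.

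The correction is still worth making before scoring: the primary endpoint should have one rule, and the remedy is cheap.

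**What to change.** In 6.2:

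1. Replace the bracketed list with the 2.2 definition word for word: the need-based wording and the full list of supports including the non-rebreather mask. Add that mechanical ventilation counts by any airway. This also aligns the two terms for ventilation and restores the missing mask in the same edit.
2. Define failure as every patient who is not a success, in place of a second device list.
3. Add one sentence: a patient alive at Day 28 from whom listed support was withdrawn or withheld as a limit of care, while still needed, is scored as a failure.

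Add one Day-28 CRF item recording whether listed support was withdrawn or withheld as a limit of care. Complete it whether the patient is admitted or discharged, as 4.5.6 already requires for the ordinal scale.

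The cost is two or three sentences and one CRF item, with no extra patients or procedures and no change to the stated sample size or power. The downside is that the success rate may be slightly lower. This concerns only how the endpoint is classified, not how patients are treated.

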4.1.2 Exclusion Criteria

Patients who meet any of the following criteria will be excluded from study entry:

General

- Current participation in another investigational drug study within the prior 7 days
- Known hypersensitivity or allergy to any ingredients of tenecteplase
- Active internal bleeding
- Known bleeding diathesis

Tenecteplase-Icahn School of Medicine at Mount Sinai
Protocol ML42492

- Use of one of the new oral anticoagulants within the last 24 hours (dabigatran, rivaroxaban, apixaban, edoxaban)
- Treatment with a thrombolytic within the last 3 months prior to randomization (exception for the use of Cathflo alteplase for occlusions of central venous catheters)
- Baseline platelet count <80,000/µL (results must be available prior to treatment)
- Baseline blood glucose >400 mg/dL (22.20 mmol/L)
- Baseline blood glucose <50 mg/dL needs to be normalized prior to randomization
- Intracranial or intraspinal surgery or trauma within 2 months
- Other, non-COVID-19 related, serious, advanced, or terminal illness (investigator judgment) or life expectancy is less than 6 months
- History of acute ischemic stroke in the last 90 days
- History of intracranial bleeding, including hemorrhagic stroke
- Presumed septic embolus; suspicion of bacterial endocarditis
- Mechanical ventilation > 48 hours, HFNC, NIPPV, NRB, or any combination, for greater than 96 hours
- Mechanical ventilation, HFNC, NRB, or NIPVV (for reasons other than obstructive sleep apnea) within the prior 30 days (excluding 96 hours prior to randomization)
- Moribund status suggesting imminent vascular collapse and inability to survive > 72 hours (investigator determination)
- Uncontrolled hypertension defined as systolic BP > 180 mm Hg and/or diastolic BP > 110 mm Hg
- Age > 75 years
- History of traumatic brain injury within 2 months
- Recent head trauma with fracture or brain injury
- History of Heparin Induced Thrombocytopenia (HIT) and/or other hereditary or acquired hemorrhagic diathesis or coagulation factor deficiency
- INR > 2 or recent oral anticoagulant therapy with INR >1.7
- Pregnancy or lactation within the prior 30 days; women of childbearing age (<55 years old) should have documentation of a negative pregnancy test
- Chronic liver disease defined as > Childs-Pugh Class B
- Patients with history of atrial fibrillation, mitral stenosis, or known left heart thrombosis
- Atrial fibrillation, mitral stenosis, or known left heart thrombosis

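### NIPPV for obstructive sleep apnea is exempted at entry but not in the primary outcome, so a recovered patient using it at day 28 fails under 6.2 and may pass under 2.2 and 2.3

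*Combined protocol and SAP*

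**What the plan says.** **Entry.** Section 4.1.2 excludes patients with "Mechanical ventilation, HFNC, NRB, or NIPVV (for reasons other than obstructive sleep apnea) within the prior 30 days", apart from the 96 hours before randomization (NIPPV is misspelled there). Support for OSA therefore does not exclude under this criterion, and the wording treats such support as a form of NIPPV. The bullet just before it excludes "Mechanical ventilation > 48 hours, HFNC, NIPPV, NRB, or any combination, for greater than 96 hours", with no mention of OSA.

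**Outcome.** Section 2.2 defines freedom from respiratory failure as "not requiring non-rebreather, high-flow nasal cannula, non-invasive positive pressure ventilation, or mechanical ventilation", and 2.3 repeats it. The secondary outcome in 2.3 follows the same pattern: "respiratory failure-free days (not requiring NRB, HFNC, NIPPV, or mechanical ventilation"). Section 6.2, which governs the primary analysis, uses different words. Besides survival, its success criterion is "free of respiratory failure (no use of HFNC, NIPPV, Intubation"). Anyone who does not meet it, which expressly includes every patient on NIPPV, counts as a failure. None of these definitions mentions OSA.

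**Data.** Section 4.5.2 records NIPPV by its settings (rate, IPAP, EPAP, FiO2), and no field is listed for the reason for use. Section 4.5.6 collects respiratory status at day 28 only in patients still admitted; the ordinal scale is completed in everyone. The Appendix 1 footnote ends daily respiratory status at a two-point ordinal improvement, day 27, death or discharge.

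**The concern.** The entry criterion accepts that NIPPV for OSA is not evidence of recent respiratory failure. The outcome drops that distinction. A patient who recovers fully and uses NIPPV at night for long-standing OSA is a failure under 6.2, whatever the study drug did. The same patient can be called a success under 2.2 and 2.3 by anyone who reads *requiring* as tied to respiratory failure. Two sites following the protocol in good faith could classify identical patients differently.

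Two things are at stake: the consistency of the primary outcome, and the size of the measured difference. Section 3.3 says the trial is meant to estimate a benefit signal for a phase III trial, so a diluted estimate matters even though the study is not powered for significance. Respiratory failure-free days have the same gap for any NIPPV that is recorded.

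**Working it through.** **1. The definitions applied to one patient.** Take a patient alive at day 28, recovered from COVID-19, using NIPPV only for OSA that predates admission.

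| Section | Test | Result |
|---|---|---|
| 4.1.2, prior-30-day bullet | NIPPV for a reason other than OSA? | Not excluded |
| 2.2 and 2.3 | Requires NIPPV? | Depends on the reader |
| 6.2 | Any use of NIPPV? | Failure |

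The mismatch is established by the text; no calculation is needed for it. The rest gives its possible size.

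**2. The plan's own power.** Inputs from 6.1: 15% good outcome on control, an absolute difference of 35 points (so 50% on tenecteplase), 40 v 20 combined and 20 v 20 for each dose, two-sided Fisher's exact test at 0.05. The exact power is

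Power = Σₐ Σ_b Bin(a; n_T, p_T) · Bin(b; n_C, p_C) · 1[Fisher p(a,b) ≤ 0.05].

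This gives 74.5% for 40 v 20 and 57.3% for 20 v 20. The plan states about 70% and 55%. A continuity-corrected normal approximation gives 67.7% and 52.8%, so the stated figures lie between the two methods and match neither closely. The point does not depend on this gap.

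**3. Effect of the missing exemption.** The documents do not say how many patients would be affected. Assumption: a share f of true successes, equal in all arms, is scored as failure only because of OSA use. Each rate becomes p(1 − f), and the difference becomes 35(1 − f) points. Expected true successes are 40 × 0.50 = 20 on tenecteplase and 20 × 0.15 = 3 on control.

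| f | Tenecteplase v control | Difference (points) | Power 40 v 20 | Power 20 v 20 | Successes lost (of 20 / of 3) |
|---|---|---|---|---|---|
| 0 | 50.0% v 15.0% | 35.0 | 74.5% | 57.3% | 0 / 0 |
| 2% | 49.0% v 14.7% | 34.3 | 73.1% | 55.8% | 0.4 / 0.06 |
| 5% | 47.5% v 14.25% | 33.25 | 70.9% | 53.4% | 1.0 / 0.15 |
| 10% | 45.0% v 13.5% | 31.5 | 67.0% | 49.4% | 2.0 / 0.3 |

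With the continuity-corrected approximation, the 40 v 20 power falls from 67.7% to 58.1% at f = 10%. That is a loss of 9.6 points, against 7.5 with the exact test.

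**4. Type I error.** If the drug has no effect and f is equal across arms, both arms share one lower success rate. The exact 40 v 20 rejection rate is 3.4% at a common rate of 15% and 3.3% at 13.5%, both below 5%.

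**5. Individual patients.** One patient is 1/20 = 5 points in a group of 20 and 1/40 = 2.5 points in the combined arm. At the expected counts (20/40 v 3/20) the Fisher p-value is 0.011. With two treated successes lost (18/40 v 3/20) it is 0.025.

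**The case against.** The strongest case is that the gap is one of wording and that sensible sites would close it. Section 2.2 is the formal definition and speaks of requiring support; 6.2 looks like shorthand, since it omits the non-rebreather and writes intubation for mechanical ventilation. That has force, but it does not settle the matter. Section 6.2 is the scoring rule for the primary analysis, and 2.2 defines failure by device rather than by reason for use.

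Three stronger readings are tempting, and the documents do not support them.

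- *A reader might infer that a recovered OSA user can never be a primary success.* That is firm only under 6.2. Under 2.2 and 2.3 the same patient may count as a success.
- *A reader might infer that home use will always be seen and scored, or that every night at home costs a respiratory failure-free day.* After discharge only the ordinal scale is required at day 28, its levels are not given, and daily respiratory status ends at discharge at the latest. Home use may simply be missed.
- *A reader might infer that the plan clearly enrols chronic users and counts all their devices.* The bullet on more than 96 hours has no OSA exception and, read literally, could exclude some of them. That reading would leave the exemption in the next bullet with little purpose, and the inclusion criterion ties the 96 hours to COVID-19 respiratory failure. Still, the text does not resolve it. Nor do the documents say whether CPAP counts as NIPPV.

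The size is also hypothetical. It rests on an assumed share, and on the 6.1 rates being free of this misclassification.

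**Conclusion.** The mismatch is real. As written, 6.2 scores a recovered patient using NIPPV only for pre-existing OSA at day 28 as a failure, while 2.2 and 2.3 leave room for the opposite. Incomplete capture after discharge adds to the inconsistency.

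The effect is probably modest. If 2% to 10% of true successes were misclassified equally across arms, the measured difference would lose 0.7 to 3.5 points, and exact power for the combined comparison would lose about 1.4 to 7.5 points. If only some users are enrolled, detected and scored as failures, the loss is smaller. With use equal across arms this is attenuation, not inflation of type I error; chance imbalance in so small a trial could move the estimate either way. It is a cheap improvement and not a must-fix.

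**What to change.** - In 2.2, 2.3 and 6.2, and for respiratory failure-free days, state that NIPPV used only for OSA documented before admission is not respiratory failure. Say whether CPAP is counted as NIPPV; if it is, cover it in the same clause.
- Use the same *requiring* wording in all three sections, so that 6.2 no longer applies a different test from 2.2.
- Record OSA device use before admission at screening, and the reason for any NIPPV use, including at day 28 after discharge.
- Reconcile the exclusion for more than 96 hours of support in 4.1.2 with the OSA exemption in the next bullet.

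The cost is one clause in each section, one or two CRF fields and a site statement of the reason for use. Tying the exemption to documentation from before admission guards against relabelling NIPPV once the outcome is known.
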